6.3.3.3 Pain Freedom at 2 Hours

The number and percentage of subjects in the treated population that experience pain freedom at 2 hours post-dose are analyzed after first imputing missing data at 2 hours to be failure (NC [Non-completer] = F [Failure]). Additionally, subjects who use rescue medication on or before assessment of pain at 2 hours are also assigned as failures (RM [Rescue medication use] = F). If the time of first rescue medication is missing, subjects are considered as failures if the date of rescue medication is the same as the date of dosing.

The analysis is done using Mantel-Haenszel risk estimation after imputation is done, with the stratification factor as yes/no for use of daily medications / oral devices to reduce the intensity of TMD symptoms. If one category of stratification factor has sparse data (less than 5 subjects), then the stratification factor is removed. Pain freedom is defined as an NRS score of zero at 2 hours post-dose (yes or no).

Results presented from the analysis includes the following:

- Response rate (i.e., “n/N” and percentage), asymptotic standard error (ASE), and 95% CI by randomization stratum for each treatment group
- Response rate (i.e., “n/N” and percentage), ASE, and 95% CI for each treatment group
- Percentage difference between treatment groups (rimegepant – placebo), ASE and 95% CI by randomization stratum
- Stratified percentage difference between treatment groups (rimegepant – placebo), ASE and 95% CI

A forest plot is produced depicting the risk difference for pain freedom at 2 hours post dose. The risk difference for each stratum will be presented, as well as the overall common risk difference.

6.3.3.4 *Time to Onset of Meaningful Pain Relief*

Time to onset of meaningful pain relief post-dose is analyzed descriptively for the treated population using Kaplan-Meier methods. Meaningful pain relief is considered the event in these analyses and is defined as the first nominal timepoint at which a 30% reduction of pain from baseline on the NRS is achieved. For clarity, meaningful pain relief is a 2-point reduction in NRS (0-10) score for subjects with a baseline pain score of 6, 7, or 8, and a 3-point reduction in NRS (0-10) score for subjects with a baseline pain score of 9 or 10.

The survival distributions will be described at the nominal timepoints of 15, 30, 45, 60, 90, and 120 minutes, and 4, 8, and 24 hours post-dose. Subjects are considered to have an event through 24 hours if the first post-dose eDiary finding date/time where meaningful pain relief is achieved is (1) at or before the upper bound of the 24-hour analysis window in minutes (see [Table 5: Analysis Visit Windows for Safety Parameters](#)), and (2) is before the imputed rescue medication start date/time, if not missing (see Section 7.1). Subjects who do not have the event through 24 hours (even in the case of missing data) are censored at the earliest of the following: (1) upper bound of the 24-hour analysis window + 1 minute; (2) time from the study drug start date/time to the imputed rescue medication start date/time, if the time is at or before the upper bound of the 24-hour analysis window in minutes; (3) time from the study drug start date/time to the last non-missing eDiary date/time defining the endpoint, if the time was before the lower bound of the 24-hour analysis window in minutes. Likewise, subjects who take rescue medication will be censored at the time of first rescue medication use, if rescue medication is taken before meaningful pain relief is recorded.

A Kaplan-Meier (KM) plot and table using the following time intervals post-dose will be generated: using the following time intervals post-dose: 0 to 15, >15 to 30, > 30 to 45, > 45 to 60, > 60 to 90, > 90 to 120, > 120 to 180, > 180 to 240, > 240 to 360, > 360 to 495, and > 495 minutes. The KM plot displays the percentage of subjects with meaningful pain relief within 24 hours on the y-axis versus time in minutes on the x-axis. Refer to Core SAP for more details.

A time-to-event distribution table will be generated. This includes number and percentage of subjects with events; number and percentage of subjects censored in or before the last time interval; number and percentage of subjects censored in the last time interval; time-to-event median with 95% CI, first quartile, and third quartile. The 95% CI for the median is estimated using the method of Brookmeyer and Crowley.

6.3.3.5 *Time to Onset of Initial Pain Relief*

The analysis in Section 6.3.3.4 will be repeated with respect for the time to onset of initial pain relief. Initial pain relief will be defined as the timepoint at which a 1-point reduction of pain from baseline NRS is achieved.

6.3.3.6 *Rescue Medication Use within 24 Hours*

The number and percentage of subjects that use rescue medication within 24 hours post-dose are analyzed. Subjects who used rescue medication as of 24 hours post-dose are deemed failures, and subjects who did not use rescue medication as of 24 hours are deemed successes. For clarity, failure is the event being modeled (i.e. rescue medication use within 24 hours) in this analysis.

Refer to Section 6.2.6.3 for the definition of rescue medication. A rescue medication would be deemed used as of 24 hours post-dose if the date/time of first rescue medication use is strictly } 24 hours after the date/time of dosing, notwithstanding Section 6.3.1 of the SAP. Subjects with a rescue medication start date on or before study drug start date/time + 24 hours and missing rescue medication start time are excluded. Subjects who report non-study medication on the Rescue Medication CRF with a missing rescue medication date, or a partial medication date that is consistent with being used within 24 hours of dosing, are also excluded. Regardless of the foregoing, if a subject has at least one rescue medication use with non-missing start time that is } 24 hours after the date/time of dosing, the subject will be included in the analyses and deemed a failure.

No analysis window around the 24-hour post-dose time point is used.

The analysis follows the same methodology set forth in Section 6.3.3.3. A forest plot is produced depicting the risk difference for rescue medication use within 24 hours post dose. The risk difference for each strata will be presented, as well as the overall common risk difference.

Time to rescue medication use through 24 hours post-dose is assessed by treatment group as follows:

- Kaplan-Meier plot and table using 2-hour time intervals (i.e., 0 to 2, > 2 to 4, ... , > 24). The Kaplan-Meier plot displays the percentage of subjects taking rescue medication

data without imputation and regardless of rescue medication use. In these tables of safety parameters, if a subject has multiple values in the end of treatment analysis visit window (see Section 7.3), then the last non-missing value measured in the analysis period is used. See Sections 6.3.4.1, 6.4.4.1, and 6.4.2.4 for further handling of ties on the same measurement date or time.

By-subject listings of safety parameters are described in subsections and identify on-treatment data.

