1 BACKGROUND AND RATIONALE

This document presents the statistical analysis plan (SAP) for Protocol BHV3000-317: A Phase 2/3, Double-Blind, Randomized, Placebo-Controlled, Safety and Efficacy Trial of BHV-3000 (rimegepant) Orally Disintegrating Tablet (ODT) for the Acute Treatment of Temporomandibular Disorders (TMD).

This SAP contains the analysis details and methodology to answer the study objectives, including planned tables, listings, and figures (TLFs), which provide the basis for the results section of the clinical study report (CSR).

The Rimegepant (BHV3000)/Zavegepant (BHV3500) Core Statistical Analysis Plan, v3.0 (the “Core SAP”) describes analysis details and methodologies common to the BHV3000 program and is incorporated by reference. The Core SAP assumes primacy for any matter where this SAP is silent (and the relevant content of the Core SAP could feasibly apply) or where the Core SAP is directly referenced as applicable. Otherwise, should any discrepancy exist between the Core SAP and this SAP, this SAP assumes primacy.

For purposes of applying the Core SAP, the following applies:

- BHV3000-317 is a single-dose study
- BHV3000-317 is not a study with a follow-up phase
- References in the Core SAP to “studies with a COVID-19 Visit Impact CRF” will not necessarily apply to BHV3000-317. COVID-19 impact will be addressed as specified in this SAP.

Note that the study was terminated prematurely in 1Q2023 due to low enrollment. As a result, the SAP is being amended from Version 1.0 to 2.0 to reduce the number of TLFs to focus only on the most important outputs.

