5 SAMPLE SIZE, POWER, AND TYPE I ERROR

If 80% of the 200 randomized (100 per treatment arm) treat with study drug, we expect roughly 160 total or 80 per treatment group in the randomized and treated population for analysis.

Assuming rimegepant provides a 2-point reduction in NRS pain, and a 1.5-point advantage over placebo on the primary endpoint, and a common standard deviation of 3.0, then the study will have roughly 88% power on the primary endpoint.

Type 1 error is not applicable. The significance of the primary and secondary endpoints will not be evaluated.

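### SAP 6.3.3.3 names no small-sample interval for pain freedom; the Wald limits it implies can collapse to zero width or under-cover in small stratum cells

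*SAP*

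**What the plan says.** SAP section 1 records that "the study was terminated prematurely in 1Q2023 due to low enrollment" and that version 2.0 was written as a result. Section 5 of the SAP states that significance will not be evaluated for the primary or secondary endpoints.

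For pain freedom, SAP 6.3.3.3 says: "The analysis is done using Mantel-Haenszel risk estimation after imputation is done". The listed output includes a rate with "asymptotic standard error (ASE), and 95% CI by randomization stratum for each treatment group", the same for each arm overall, "Percentage difference between treatment groups (rimegepant – placebo), ASE and 95% CI by randomization stratum", and a stratified difference with its standard error and interval. A forest plot shows each stratum and the common risk difference.

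The only sparse-data rule is: "If one category of stratification factor has sparse data (less than 5 subjects), then the stratification factor is removed". It counts subjects in a category of the factor. It does not count subjects per arm or responders.

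For rescue use, SAP 6.3.3.6 says: "The analysis follows the same methodology set forth in Section 6.3.3.3", with a forest plot of its own.

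The formula for the 95% limits is not given. SAP section 1 lets the Core SAP govern wherever this SAP is silent.

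**The concern.** An asymptotic standard error printed beside each interval, with no other method named, points to limits of estimate ± 1.96 × standard error (Wald). That form fails in small cells with low rates. Pain freedom means a score of exactly 0 two hours after dosing at a score of 6 or more, and missing scores and early rescue count as failures, so cells with few or no responders are plausible. With none, the estimated standard error is 0 and the interval is 0% to 0%.

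The sparse-data rule does not prevent this. A stratum of 5 or 6 subjects, about 2-3 per arm, would still be reported and plotted, and the rule gives the overall arm rates no protection at all.

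With testing dropped, the estimates and intervals are all the inference that remains for these endpoints. A zero-width or far too narrow interval in a forest plot would convey precision that the data do not have.

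**Working it through.** **Inputs from the documents.** Allocation 1:1 (SAP 2.2). Planned size: "we expect roughly 160 total or 80 per treatment group in the randomized and treated population for analysis" (SAP 5). Stratum retention threshold: 5 subjects (SAP 6.3.3.3). Final N, stratum sizes, pain-freedom rates and rescue rates are not given, so those below are assumptions shown as ranges.

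**The plan's own sizing figure.** It concerns the primary endpoint only: difference 1.5, SD 3.0, 80 per arm, two-sided 0.05. The standard error is 3.0 × √(2/80) = 0.474, and 1.5/0.474 = 3.162. Power = Φ(3.162 − 1.960) = 88.5%, against a stated figure of roughly 88%. It reproduces. No sizing is given for pain freedom or rescue use.

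**Single rate.** Wald limits are p̂ ± 1.96 × √(p̂(1 − p̂)/n). Coverage is the sum of binomial probabilities over the counts x whose interval contains the true rate.

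Worked case, n=5, true rate 10%:
- x=0: 0 to 0, misses.
- x=1: 0.20 ± 0.351, covers.
- x=2: 0.40 ± 0.429, covers.
- x=3: 0.60 ± 0.429, lower limit 0.171, misses. Higher counts miss too.
- Coverage = 0.328 + 0.073 = 40.1%. The chance of a zero-event cell is 0.9^5 = 59.0%.

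| n in cell | Wald coverage, true rate 5% | 10% | 20% |
|---|---|---|---|
| 5 | 22.5% | 40.1% | 66.6% |
| 10 | 40.0% | 65.0% | 88.6% |
| 20 | 63.9% | 87.6% | 92.1% |
| 40 | 86.8% | 91.4% | 90.5% |

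For n = 5 to 20 and rates of 5-10%, Wilson coverage is 91-98% and Clopper-Pearson 98-99%.

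**Risk difference within a stratum.** Wald limits are d ± 1.96 × √(p̂1(1 − p̂1)/n + p̂2(1 − p̂2)/n), enumerated over both arms. The interval has zero width only if both arms are at 0% or 100%. For 10% versus 5% the chance is essentially 0.90^n × 0.95^n: at n=5, 0.590 × 0.774 = 45.7%.

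| n per arm | 10% vs 5%: coverage (zero width) | 20% vs 10% | 40% vs 50% |
|---|---|---|---|
| 5 | 52% (46%) | 74% (19%) | 86% (0.6%) |
| 10 | 75% (21%) | 88% (4%) | 91% (about 0) |
| 20 | 86% (4%) | 94% (0.1%) | 93% (0) |
| 40 | 94% (0.2%) | 94% (0) | 94% (0) |

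Newcombe coverage for 10% versus 5% is 99.9%, 99.5%, 98.6% and 96.2% at 5, 10, 20 and 40 per arm.

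**Common Mantel-Haenszel difference.** Simulated with two strata, 200,000 draws per scenario and two standard large-sample variance formulas. For 20% versus 10%: 86-87% at 10 per arm in total, 93-94% at 20, 94% at 40. For 10% versus 5%: 75%, 86% and 94%.

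**What other limits give with no events.** The upper Clopper-Pearson limit is 1 − 0.025^(1/n). For 0/5 this is 1 − 0.025^0.2 = 52.2%, and for 0/10 it is 30.8%. Wald gives 0-0% in both.

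**The case against.** The strongest answer is that this SAP never prescribes Wald limits. A reader might infer that it does, but the standard error and the interval are listed as separate items and the Core SAP fills gaps. If the Core SAP names exact or score limits for rates, the single-rate intervals would not collapse. This stands, and it makes the conclusion conditional. It does not remove the gap in this SAP, which does name its method for the interval of a Kaplan-Meier median.

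Second, a reader might infer that the trial ended with cells of 5 to 10. The documents report low enrolment but give no final N. At 20 per arm (20% versus 10%) or 40 per arm (10% versus 5%), coverage for the difference is already about 94%, and the common difference behaves similarly. This also stands.

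Third, the low-rate figures do not carry over to rescue use. They rest on the demanding definition of pain freedom, and no document gives a rescue rate. At 40% versus 50%, coverage is 91% with 10 per arm and zero width is practically absent.

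Fourth, these are descriptive secondary summaries, and n/N is printed with each response rate, so a reader of the table would see 0/5 beside a collapsed interval. That softens the consequence. The forest plots are specified as showing risk differences, with no mention of counts.

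**Conclusion.** The point holds as a conditional weakness in interval specification, and it should be corrected. Zero width in a cell with no events, or all events, follows from the Wald formula and needs no assumed rate. How far coverage falls does depend on assumptions: Wald limits, pain-freedom rates of 5-10%, and cells of up to about 20. On those assumptions, single-rate coverage runs from 23% to 88% and coverage for a 10% versus 5% difference from 52% to 86%. By about 40 per arm the difference is close to nominal, at 94%.

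The exposure is mainly pain freedom by stratum. It is smaller for the common difference unless the whole trial is very small, and smaller for rescue use if that rate is mid-range. The documents do not support saying that the reported intervals did collapse, or that both endpoints are affected to the same degree.

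**What to change.** In SAP 6.3.3.3, name the interval methods, or cite the Core SAP section if it already does so:
- Wilson or Clopper-Pearson limits for single rates, overall and by stratum.
- Newcombe or Miettinen-Nurminen limits for stratum risk differences.
- A stratified score or stratified Newcombe interval for the common difference.

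Apply the same methods in SAP 6.3.3.6 for consistency. It would also help to count the sparse-data rule per arm within stratum.

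The cost is SAP wording and a procedure option, with no new data. The drawback is wider intervals, substantially so in zero-event cells (0/5 goes from 0-0% to 0-52% with exact limits), and some over-coverage in very small cells, such as 99.3% for Newcombe at 5 per arm with 20% versus 10%.

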9.4.3.2 Change from Baseline of Pain on NRS

The change from baseline of pain on NRS score at 2 hours post-dose will be analyzed with a generalized linear mixed effect model that includes subject as a random effect, the baseline NRS (0-10) value as a covariate, and fixed effects for treatment group, stratification factor (use of daily medications / oral devices to reduce the intensity of TMD symptoms), scheduled time point, and time point by treatment group interaction. Time points included in the model are nominally at 15, 30, 45, 60, 90 and 120 minutes post-dose. Repeated measurements within-subject will be modeled using an unstructured covariance structure for within-subject error. In the case that the model fails to converge, a Huynh-Feldt error structure will be attempted, followed by an AR(1) structure. Error degrees of freedom will be calculated using a Kenward-Roger approximation. The difference estimate (rimegepant - placebo), SE, 95% CI, and p-value will be reported for 2 hours post-dose.

Intercurrent events of use of a non-study rescue medication at or before 2 hours post-dose, or if a subject fails to log their pain score at any time after study drug is administered through 2 hours post-dose, will be handled in the same manner as they are for the primary endpoint.

9.4.3.3 *Pain Freedom at 2 Hours*

The number of subjects that are pain free at 2 hours post-dose will be analyzed after first imputing missing data at 2 hours to be failure (NC = F). Additionally, subjects who use rescue medication on or before assessment of pain at 2 hours will also be assigned as failures (RM = F). The analysis will be done using a stratified Cochran-Mantel-Haenszel (CMH) test after imputation is done, with the stratification factor as use of daily medications / oral devices to reduce the intensity of TMD symptoms.

9.4.3.4 *Time to Onset of Meaningful Pain Relief*

Time to onset of meaningful pain relief post-dose will be defined as the first nominal timepoint at which a 30% reduction of pain from baseline on NRS is achieved. This will be analyzed using Kaplan-Meier methods for a “time to event” analysis. Rimegepant will be compared to placebo using a log-rank test which will compare the survival distributions. Intercurrent events will be handled in the same manner as they are for the primary endpoint.

9.4.3.5 *Time to Onset of Initial Pain Relief*

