3.2.2 Secondary Objective Estimands

Table 2: Secondary Objective Estimands

1	Objective	To evaluate rimegepant compared with placebo on the time-weighted sum of pain intensity difference (SPID) from baseline scores for the first 24 hours post-dose (SPID-24).
	Efficacy Endpoint	Difference in SPID-24 scores between rimegepant and placebo assessed across the first 24 hours post-dose in treated subjects
	Summary	Same as that of primary estimand, with respect to time-weighted SPID-24.
	Intercurrent Events	Same as that of primary estimand.
2	Objective	To evaluate rimegepant compared to placebo on change from baseline on NRS (0-10) score at 2 hours post-dose.
	Efficacy Endpoint	Change from baseline in NRS score to 2 hours post-dose in treated subjects.
	Summary	Difference in change from baseline in the NRS score between the rimegepant and placebo groups using a generalized linear mixed effect model.

	Intercurrent Events	Same as that of primary estimand.
3	Objective	To evaluate rimegepant compared to placebo on the proportion of subjects that are pain free at 2 hours post-dose.
	Efficacy Endpoint	The percentage of treated subjects that report no pain at 2 hours post-dose
	Summary	The difference between the rimegepant and placebo group in the percentage of subjects who are pain-free at 2 hours post-dose, analyzed using Mantel-Haenszel risk estimation. The definition of “pain free” is a subject that reports a zero on their 2 hour post-dose NRS assessment.
	Intercurrent Events	1) Use of non-study rescue medications on or before two hours post-dose Composite strategy: Subjects who use rescue medication on or before assessment of pain at two hours are imputed as a failure. 2) Failure to report eDiary assessments at two-hours post-dose Composite strategy: Subjects with missing data at two hours post-dose are imputed as a failure. 3) All other intercurrent events: Treatment policy strategy: All available assessments on the subject are used regardless of other intercurrent events.
4	Objective	To evaluate rimegepant compared to placebo on time to onset of meaningful pain relief post-dose.
	Efficacy Endpoint	The time to first nominal timepoint at which pain on NRS (0-10) decreases by 30% from baseline in treated subjects.

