	Summary	Descriptive analysis by treatment group of the time to first nominal timepoint at which pain on NRS (0-10) decreases by 30% from baseline using Kaplan-Meier method. Meaningful pain reduction will be measured as a two-point reduction in NRS (0-10) score for subjects with a baseline pain score of 6, 7, or 8 and a 3 point reduction in NRS (0-10) score for subjects with a baseline pain score of 9 or 10.
	Intercurrent Events	1) Use of non-study rescue medications on or before onset of meaningful pain relief Composite strategy: Subjects who use rescue medication on or before onset of meaningful pain relief are censored at the time of rescue medication use. 2) Failure to report eDiary assessments. Composite strategy: Subjects who do not complete all post-dose assessment will be censored at the time of the last completed NRS pain assessment. 3) All other intercurrent events: Treatment policy strategy: All available assessments on the subject are used regardless of other intercurrent events.
5	Objective	To evaluate rimegepant compared to placebo on time to onset of initial pain relief post-dose.
	Efficacy Endpoint	The time to first nominal timepoint at which pain on NRS (0-10) decreases by 1 point from baseline in treated subjects.
	Summary	Descriptive analysis by treatment group of the time to first nominal timepoint at which pain on NRS (0-10) decreases by 1 point from baseline using the Kaplan-Meier method.

Intercurrent Events	Same as secondary endpoint # 4
---------------------	--------------------------------

6	Objective	To evaluate rimegepant compared to placebo on the probability of requiring rescue medication within 24 hours of initial treatment.
	Efficacy Endpoint	Percentage of treated subjects that use rescue medication within 24 hours after administration of study drug.
	Summary	The difference in the percentage of subjects that take study drug and then take rescue medication within 24 hours, analyzed using Mantel-Haenszel risk estimation.
	Intercurrent Events	Treatment policy strategy : All available assessments on the subject are used regardless of intercurrent events.

CCI [REDACTED]

[REDACTED]

[REDACTED]

[REDACTED]

[REDACTED]

[REDACTED]

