6.3.3.2 Change from Baseline of Pain on NRS at 2 Hours

Change from baseline pain on NRS score is analyzed on the treated population using a generalized linear mixed effect model that includes the baseline NRS (0-10) value as a covariate, and fixed effects for treatment group, stratification factor (use of daily medications / oral devices to reduce the intensity of TMD symptoms), scheduled time point, and time point by treatment group interaction. Time points included in the model are nominally at 15, 30, 45, 60, 90 and 120 minutes post-dose.

Repeated measures within subject are modeled using an unstructured covariance structure for within subject error. In the case the model fails to converge, a Huynh-Feldt error structure is utilized, followed by an AR(1) structure. Error degrees of freedom are calculated using the Kenward-Rogers approximation if an unstructured covariance structure fits appropriately; otherwise, a sandwich estimator is utilized to estimate the covariance structure, and the degrees of freedom are calculated using the between-within method.

Restricted maximum likelihood (REML) estimation is utilized; should the model fail to converge under REML, maximum likelihood estimation is utilized.

Least squares (LS) means, SE, and 95% CIs are reported for each treatment group at 2 hours post-dose, along with LS mean difference estimate (rimegepant - placebo) and associated SE and 95% CI.

Intercurrent events will be handled in the same way as in the primary analysis described in Section 6.3.2.1.

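### Secondary objectives 4 and 5 compare rimegepant with placebo on time to relief, but the SAP plans no between-group estimate with a confidence interval for either

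*SAP*

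**What the plan says.** SAP Table 2 words both objectives as comparisons. Objective 4 is "To evaluate rimegepant compared to placebo on time to onset of meaningful pain relief post-dose" and objective 5 is "To evaluate rimegepant compared to placebo on time to onset of initial pain relief post-dose". Protocol 9.4.3.4 and 9.4.3.5 planned to meet them with a test: "Rimegepant will be compared to placebo using a log-rank test which will compare the survival distributions".

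SAP v2.0 is still based on protocol version 3.0. Its revision history records that the log-rank comparison was removed for both objectives. The summary attribute in Table 2 now reads, for objective 4, "Descriptive analysis by treatment group of the time to first nominal timepoint at which pain on NRS (0-10) decreases by 30% from baseline" and, for objective 5, "Descriptive analysis by treatment group of the time to first nominal timepoint at which pain on NRS (0-10) decreases by 1 point from baseline", each by the Kaplan-Meier method. Section 6.3.3.4 says the same: "Time to onset of meaningful pain relief post-dose is analyzed descriptively for the treated population using Kaplan-Meier methods". Section 6.3.3.5 follows it: "The analysis in Section 6.3.3.4 will be repeated with respect for the time to onset of initial pain relief".

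The output planned for each arm consists of:
- a Kaplan-Meier plot and a table over eleven time intervals;
- a description of the survival distribution at each of the nine post-dose diary times;
- counts of events and of censored subjects;
- the median with a 95% CI, and the quartiles.

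No hazard ratio, difference in proportions, difference in medians or difference in restricted mean time is specified. SAP section 5 says that significance will not be evaluated for the primary or secondary endpoints.

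**The concern.** SAP 3.2 defines an estimand as what is estimated to answer the question posed by the objective. For objectives 4 and 5 the question is a contrast between arms, but the summary attribute contains no contrast. The other endpoints were handled differently: they lost their p-values and kept the estimate. For the 2-hour change, for example, the SAP still reports arm-level means "along with LS mean difference estimate (rimegepant - placebo) and associated SE and 95% CI".

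At stake is what the report can say about speed of relief. Arm medians come from a few diary times, so they will cluster, can nearly coincide (most easily with the 1-point threshold), and may not be reached. Readers are then likely to judge the comparison by whether two arm-level intervals overlap, and that is not an interval for the difference. In a small, terminated trial the width of that interval is the most useful thing to report, because it shows how little can be concluded.

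**Working it through.** **The plan's own figure.** The only design figure is power of roughly 88% for the primary endpoint (SAP section 5: 80 per arm, difference 1.5, SD 3.0; two-sided 0.05 from protocol 9.4.4).
- SE of the difference = 3.0 × √(2/80) = 0.474.
- 1.5/0.474 = 3.16, and 3.16 − 1.96 = 1.20, which gives 88.5% (88.2% with the t distribution).

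The figure reproduces. It has no bearing on time to relief, for which the documents give no event rate, effect or number actually treated.

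**Side-by-side check of SAP v2.0**

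| Endpoint | Between-group estimate with 95% CI | Place |
|---|---|---|
| Primary, SPID-2 | LS mean difference | 6.3.2.1 |
| 1, SPID-24 | same analysis repeated | 6.3.3.1 |
| 2, change at 2 hours | LS mean difference | 6.3.3.2 |
| 3, pain freedom at 2 hours | stratified percentage difference | 6.3.3.3 |
| 4, meaningful relief | none | 6.3.3.4 |
| 5, initial relief | none | 6.3.3.5 |
| 6, rescue within 24 hours | stratified difference, method of 6.3.3.3 | 6.3.3.6 |

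Four of six secondary objectives have a contrast and two do not. Section 6.3.3.6 also plans Kaplan-Meier output for time to rescue, so the SAP already pairs such curves with a risk difference.

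**What an interval would look like.** Assumed, not from the documents: relief by 2 hours of 45% on placebo and 65% on rimegepant, with no censoring and no stratification.
- SE = √[(0.45 × 0.55 + 0.65 × 0.35)/n] = √(0.475/n).
- n = 80 per arm (planned): SE 0.077, × 1.96 = ±15.1 points.
- n = 40 (assumed): SE 0.109, ±21.4 points.
- n = 20 (assumed): SE 0.154, ±30.2 points.

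On the hazard-ratio scale, SE(log HR) = 2/√events under 1:1 allocation. The 95% limits are the estimate divided and multiplied by 2.40 at 20 total events, 1.86 at 40, 1.55 at 80 and 1.36 at 160. These event counts are also assumed, the last being every planned treated subject.

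**Two timing rules that affect a 2-hour contrast**
- SAP Table 5 lets the 2-hour diary be saved from 115 to 135 minutes, and 6.3.3.4 judges events by the diary's date and time. A cut at exactly 120 minutes would miss relief reported on a valid 2-hour diary saved at 121 to 135 minutes.
- SAP 7.1.5 sets a rescue with a missing time on the dosing date to the dose time. Under the censoring rule in 6.3.3.4 such a subject is censored at time zero, even if rescue came hours later.

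**The case against.** The strongest reply is that the change is deliberate, disclosed and coherent. The trial stopped early, v2.0 was cut back to the most important outputs, no endpoint is tested, and Table 2 openly calls both summaries descriptive. On that view only the wording of the objectives, carried over from the protocol, is out of step. This stands as far as the test is concerned: the missing p-value is not a defect. It does not explain why estimation was kept for every other endpoint and dropped for these two. Section 5 rules out significance, not estimates.

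A reader might infer that objectives 4 and 5 cannot be answered at all, or that only two medians will be shown. The documents do not support either reading. Section 6.3.3.4 plans descriptions at each diary time and an interval table, so a point difference can be had by subtraction. What is absent is a planned contrast with its uncertainty.

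It is also fair to say that the interval will be wide after low enrolment. That limits what it can show, but a reader still needs to see it.

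Finally, Kaplan-Meier details are referred to the Core SAP, which is not available here. It governs where this SAP is silent or refers to it, and this SAP expressly specifies a descriptive analysis by arm. If its tables print arm-level standard errors, a reader could build an unstratified interval, but that would not be a planned analysis.

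**Conclusion.** The point holds as a gap in estimation. Two of the six secondary objectives remain comparative with no planned between-group estimate or CI, while the other four and the primary have one. It is a modest gap and cheap to close: no conclusion on the primary endpoint depends on it, and informal comparison remains possible.

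The count of two in six rests on the SAP text alone, with the reservation that the Core SAP could not be read. The ±15 to ±30 points rest on assumed relief rates and, below 80 per arm, on assumed sample sizes. A reader might take them as a property of this trial. They are not, because the documents give neither the relief rates nor the number treated.

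**What to change.** In SAP 6.3.3.4, 6.3.3.5 and Table 2 objectives 4 and 5, add without a p-value the difference (rimegepant minus placebo) in the Kaplan-Meier proportion with relief by the 2-hour diary, with its 95% CI. Specify that:
- the horizon is the nominal 2-hour assessment, with the window's upper bound of 135 minutes, so that reports saved at 121 to 135 minutes count;
- the estimate is stratified by the randomisation stratum, with the rule for combining strata stated and the sparse-data rule of 6.3.3.3 applied (stratification removed if a category has fewer than 5 subjects);
- the number of subjects censored at dose time because a same-day rescue time is missing is reported by arm.

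A difference in restricted mean time to relief over the same horizon is optional. Both quantities are narrower than the planned follow-up through 24 hours, so the existing Kaplan-Meier output should stay. If the sponsor wants no contrast, the minimum is to state in Table 2 that objectives 4 and 5 are now descriptive only.

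The cost is a little programming, because the planned curves are not stratified, plus an added row or so in tables already planned. No new data are needed, and the change does not conflict with the no-significance rule in section 5. The downside is a wide interval, which the report should present as such.
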